We want to investigate this hypothesis in women from 2 or 3 generations in direct link from the same family, such as grandmother, mother and daughter. At birth, mothers transmit gut bacteria to their offspring and therefore the maternal microbiome plays an important role in shaping the early composition of offspring's gut microbiota when compared to fathers. Mother's breast milk also influences the gut microbiome of their offspring in early life. However, there is little information on these maternal influences in the late life of offspring and especially in response to dietary fibre intake. Therefore, we want to determine if there is a transgenerational similarity in gut microbiome composition, metabolic profiles and clinical outcomes in response to 4-week high intake of dietary fibres compared to placebo. This approach (individuals in direct link and female participants across all generations) will allow us to 1) determine if there is a maternal influence on the gut microbiome and responses to dietary fibres of younger generations in late life and 2) have a less heterogenous cohort by focusing on women only which will allow for a better understanding of the data.

2. Study Hypothesis:

We hypothesize that compared to placebo, the dietary fibre intervention will lead to a higher production of short-chain fatty acids by the older generation's gut microbiota when compared to that of the younger generation which will translate into differential responses of gut microbiota composition, glucose, insulin, lipids, gut hormones and inflammatory markers levels.

3. Study Aim:

Investigate the effects of a dietary fibre blend taken over a 4-week period on the production of short-chain fatty acids by the gut microbiota, microbiota composition and health outcomes (glucose, insulin, lipids, gut hormones and inflammatory markers levels) of individuals from 2 or 3 generations in direct link (grandmother, mother and daughter).

4. Primary Outcome:

Comparison of the change in SCFA production from baseline to the end of the intervention between grandmothers, mothers and daughters between dietary fibre intervention and placebo.

5. Secondary Outcomes:

- Comparison of gut microbiota composition from baseline to the end of the intervention between grandmothers, mothers and daughters between dietary fibre intervention and placebo.

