- Comparison of metabolic profiles of urine and stool samples from baseline to the end of intervention between grandmothers, mothers and daughters between dietary fibre intervention and placebo.
- Comparison of blood glucose levels from baseline to the end of intervention between grandmothers, mothers and daughters between dietary fibre intervention and placebo.
- Comparison of blood insulin levels from baseline to the end of intervention between grandmothers, mothers and daughters between dietary fibre intervention and placebo.
- Comparison of gut hormone levels from baseline to the end of intervention between grandmothers, mothers and daughters between dietary fibre intervention and placebo.
- Comparison of blood lipid levels from baseline to the end of intervention between grandmothers, mothers and daughters between dietary fibre intervention and placebo.
- Correlation of 3 days food diary information with gut bacteria production of SCFA among the 2 or 3 generations.

- Correlation of 3 days food diary information with gut bacteria composition among the 2 or 3 generations.
- Correlation of 3 days food diary information with urine metabolic profiles among the 2 or 3 generations.

6. Study methodology:

- Randomised, placebo controlled, double-blinded, cross-over study
- 4 weeks intervention (dietary fibre/placebo) 4 weeks wash-out 4 weeks intervention (opposite arm of intervention)

7. Intervention products:

The fibre intervention product will contain in equal proportions inulin, pectin and oat beta-glucan.

The placebo product will contain cellulose.

The intervention products will be sourced from Nestlé.

The fibre intervention and placebo products will be powders stored in sachets that will look identical and identically-packaged and participants will be able to add them to and mix them with their meals. The amount of intervention taken daily will be increased gradually (see below) to allow participants to adapt to the increased intake of dietary fibre and reduce the likelihood of gastrointestinal discomfort.

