Participants will be asked not to consume any intervention products on the study visit. At the end of study visits 1 and 3, participants will receive 56 sachets of intervention products. At study visits 2 and 4, participants will be asked to bring the empty sachets to assess compliance with the intervention. Throughout the 2 study intervention periods, participants will be asked to complete daily the Intervention Product Reminder sheet whenever they take the intervention product. This will also allow for assessing compliance with the intervention.

Intervention products will be stored in sachets and boxes in the Commonwealth Building of Hammersmith campus, Imperial College London.

8. Participants:

10 duos or trios (20-30 participants) females

Inclusion criteria:

- Any of the following groups of people (in direct descent and from the same family):
 - Grandmother, mother and daughter

- Mother and daughter
- Grandmother and granddaughter
- Age 18-85 (inclusive)
- BMI: 18.5-30 kg/m² (inclusive)
- Considering themselves healthy

Exclusion criteria:

- Intake of antibiotics in the past 3 months and during the study
- Intake of probiotic supplements in the past month and during the study
- Regular intake of laxatives in the past month and during the study
- Subjects with the following conditions:
 - Inflammatory Bowel Disease (IBD)
 - Irritable Bowel Syndrome (IBS)
 - Coeliac Disease
 - Type 12 Diabetes
 - Any type of cancer
 - Autoimmune conditions
 - Conditions that affect the liver
 - Conditions that affect the pancreas
- Subjects who require medical intervention in the coming 3 months
- Smokers
- Shift workers
- Gluten intolerance
- Pregnant and lactating women
- Subjects living in care homes
- had weight changes >5% in the preceding 3 months
- Subjects who are unable to give informed consent by themselves
- Subjects who are currently participating in other clinical trials

Support of number of volunteers:

This is a pilot exploratory study in a new area of research and therefore statistical power calculation is not possible.

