There is a 4-week gap (28 days +/-4 days) between Study Visits 1 and 2, followed by a 4-week wash-out period (28 days +/-7 days) and then followed by Study Visits 3 and 4 (4-week gap 28 days +/-4 days between Study Visits 3 and 4) (Figure 1).

[figure not shown]

Figure 1. Diagram of study visits; V=study visit

Participants will come fasted at the Study Visits and they will not have consumed any intervention products in the morning. They will bring their stool and urine samples, the 3 days food diaries and the participants questionnaire. They will also undergo a physical examination (body weight, height and fat percentage) and have their blood pressure measured and recorded. Women of childbearing age will have a pregnancy test at the beginning of each study visit. If the pregnancy test result is positive, they will be withdrawn from the study. No more data and samples will be collected from them. All the data and samples that were collected up to their withdrawal will be used in data analysis.

At Study Visits 2 and 4 participants will be asked to complete a Visual Analogue Questionnaire where they will rate how the dietary intervention has affected various gastrointestinal symptoms, such as constipation, bloating, appetite.

At 09:30 an intravenous cannula will be inserted into one arm for blood sampling by an adequately trained doctor, nurse or member of research team under aseptic conditions. Just before 10:00 fasting blood samples will be taken through an intravenous peripheral cannula (-15min and -5min). Participants will then receive a standardised breakfast at 10:00.

Postprandial blood samples will be taken at 15, 30, 45, 60, 90, 120 180 and 240 minutes after having the standardised breakfast to measure gut hormones, lipids, glucose, and insulin and inflammatory marker levels. 10ml of blood samples will be

taken at each sampling point, and therefore 100ml (10 x 10ml) during each study visit will be taken (Figure 2).

[figure not shown]

Figure 2. Diagram of Study Visit protocol; VAS=Visual Analogue Scale

Appetite and wellbeing will be assessed at the following timepoints (Figure 2): -15, 0, 30, 60, 120,180 and 240 minutes using a visual analogue scale (VAS).

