The collected samples (stool, urine and blood) will be analysed for: gut microbiota composition (from stools) through 16S rRNA sequencing and qPCR (quantitative Polymerase Chain Reaction); metabolites produced by the gut microbiota (from stools and urine) thorough NMR (Nuclear Magnetic Resonance), GC-MS (gas chromatography coupled with mass spectrometry), LC-MS (liquid chromatography coupled with mass spectrometry), LC-MS (liquid chromatography coupled with mass spectrometry), blood glucose, insulin, gut hormones (PYY and GLP-1), inflammatory markers (C reactive protein) and lipid levels.

11. Statistical Analysis

Statistical tests, such as ANOVA (Analysis of Variance) and t-tests (paired and unpaired) will be used to compare different groups: study participants groups, dietary fibre groups and placebo groups. Correlation analysis (Pearson and/or Spearman) and linear models will be used to analyse the relationship between gut bacteria taxa, short-chain fatty acids levels, metabolites levels, food diary information and demographics. Statistical significance levels will be p<0.05.

Various platforms will be used to analyse the data. Gut microbiome composition will be analysed using 16S rRNA sequencing on Illumina MiSeq and statistical analyses will be performed in R. Species diversity and richness will be calculated and statistical tests include t-tests and Mann-Whitney U tests, statistical significance p<0.05. Species diversity and richness and their changes from baseline between grandmother, mother and offspring will be compared. Data from placebo and dietary fibre intervention will be compared.

Short-chain fatty acids (SCFA) production from stool samples will be measured using GC-MS (Gas Chromatography coupled with Mass Spectrometry). T-tests (paired and/or unpaired) and ANOVA tests will be used to determine whether there are significant differences in SCFA production between grandmothers, mothers and offspring from baseline to end of intervention. Data from placebo and dietary fibre intervention will be compared. Significance levels will be p<0.05.

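### The diet, taxa, SCFA and metabolite associations have no stated unit of analysis and no woman, family or product term, so pooling visits would make p-values too small

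*Combined protocol and SAP*

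**What the plan says.** Section 11 (Statistical Analysis) gives the method: "Correlation analysis (Pearson and/or Spearman) and linear models will be used to analyse the relationship between gut bacteria taxa", and the sentence goes on to list "short-chain fatty acids levels, metabolites levels, food diary information and demographics". The threshold follows: "Statistical significance levels will be p<0.05". Sidedness is not stated.

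Section 5 lists nine secondary outcomes. The last three relate the food diary to SCFA production, to gut bacteria composition and to urine metabolic profiles. The first of them reads "Correlation of 3 days food diary information with gut bacteria production of SCFA among the 2 or 3 generations".

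Three features of the design bear on this:

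- **Size.** Section 8 (Participants) plans "10 duos or trios (20-30 participants) females".
- **Relatedness.** The Introduction describes the participants as "women from 2 or 3 generations in direct link from the same family".
- **Repeats.** Section 9 has four study visits and says of them "They will bring their stool and urine samples, the 3 days food diaries and the participants questionnaire". Visits 1 and 3 precede an intervention period; Visits 2 and 4 end one.

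For these associations the protocol does not say which visit, average or change score is used. Nor does it name a repeated-measures method, a family term or a product term. Paired t-tests appear only for comparing groups.

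**The concern.** The usual p-value for a Pearson or Spearman coefficient assumes independent rows. Here rows can be dependent in two ways: visits from the same woman, and women from the same family. The second is not a remote possibility, since the Introduction says "we want to determine if there is a transgenerational similarity in gut microbiome composition".

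As written, an analyst could run the test on 80 to 120 rows (all visits) or on 20 to 30 rows (one per woman), and could choose after seeing the data. The choice changes the bar for significance considerably, and the larger count overstates the information when both variables are stable within woman.

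A second issue arises only with pooling. Visits 2 and 4 follow four weeks of fibre or cellulose, while Visits 1 and 3 do not. A correlation across all visits without a product term can therefore mix the effect of the intervention with the effect of diet. Section 11 does not say whether sachets are coded as part of diary intake, so the direction of that mixing is unknown.

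At stake are a third of the secondary outcomes (3 of 9) and all the taxa, SCFA and metabolite associations. The primary SCFA comparison is a separate matter.

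**Working it through.** The plan has no power or sample-size figure to reproduce; the only stated number is the 5% level. The check asks what that level becomes under each way of forming the rows.

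**Inputs from the protocol.** 10 families; m = 2 or 3 women per family; up to 4 visits; p<0.05, taken as two-sided.

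**Inputs assumed.** The protocol gives no ICCs, so a range is used, with the same value for both variables unless stated. Woman ICC (*w*) is the total correlation between two visits of one woman. Family ICC (*f*) is the correlation between two relatives and is included in *w*.

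**Formulas.** For null correlations the approximate design effect (DE) is

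- all four visits pooled: DE = 1 + 3·w_x·w_y + 4(m−1)·f_x·f_y
- one row per woman: DE = 1 + (m−1)·f_x·f_y

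The actual error is approximately 2·[1 − Φ(1.96/√DE)]. A simulation with 8,000 replicates per scenario, in which x and y are unrelated, checks this. With independent rows it returned 4.7% (80 rows) and 5.3% (120 rows), as it should.

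**All four visits pooled (Pearson)**

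| w | f | m | DE | Formula | Simulated |
|---|---|---|---|---|---|
| 0.3 | 0 | 2 / 3 | 1 + 3(0.09) = 1.27 | 8.2% | 7.8% / 8.1% |
| 0.5 | 0 | 2 / 3 | 1 + 3(0.25) = 1.75 | 13.8% | 13.7% / 13.4% |
| 0.7 | 0 | 2 / 3 | 1 + 3(0.49) = 2.47 | 21.2% | 21.1% / 21.9% |
| 0.7 | 0.3 | 2 | 1 + 1.47 + 4(0.09) = 2.83 | 24.4% | 24.8% |
| 0.7 | 0.3 | 3 | 1 + 1.47 + 8(0.09) = 3.19 | 27.3% | 27.6% |

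Spearman gave similar values, from 7.9% in the first row to 25.3% in the last. In the last row, 120 nominal rows are worth 120/3.19 ≈ 38.

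**One row per woman, all generations together**

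| f | DE, m = 2 / 3 | Formula | Simulated |
|---|---|---|---|
| 0.1 | 1.01 / 1.02 | 5.1% / 5.2% | 4.9% / 5.1% |
| 0.3 | 1.09 / 1.18 | 6.1% / 7.1% | 6.0% / 7.4% |
| 0.5 | 1.25 / 1.50 | 8.0% / 11.0% | 7.7% / 11.2% |

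**Cases that bound the result**

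- One visit within one generation means one woman per family, so both added terms vanish and the level is 5% (simulated 5.0 to 5.1%).
- If one variable has no woman or family correlation, the products are zero (simulated 4.7 to 5.3%, visits pooled).
- With unequal ICCs, for example 0.3 for diet and 0.5 for SCFA and visits pooled, DE = 1 + 3(0.15) = 1.45 and the error is about 10%.
- For a characteristic fixed within woman, such as age, pooled visits gave about 23% at outcome ICC 0.5 and 27 to 28% at 0.7.

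**What the unit of analysis does to the bar.** The smallest |r| that reaches p<0.05 if rows are treated as independent is 0.220 (80 rows) or 0.179 (120 rows), against 0.444 (20 women) or 0.361 (30 women).

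**The case against.** The strongest reply is that the plan never says visits will be pooled. That is true. A reader might infer that plain correlation is invalid however the rows are formed, but the documents do not support this. The outcomes speak of associations among the generations, and one natural reading is a separate correlation in each generation at one visit, which holds its level. Change scores, which Section 11 uses for other endpoints, also hold it (4.8 to 5.2% in simulation, even at woman ICC 0.7) if women and families differ only in their stable levels. That condition is not assured, because the Introduction also asks whether relatives respond alike to the fibre.

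Section 11 also names linear models, which could carry woman, family and product terms. As written they carry none, and the three outcomes are themselves worded as correlations.

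The sizes depend on assumed ICCs, and the highest figures need pooling plus high ICCs in both variables. This stands.

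On product, a reader might set the 30 g/day of Section 7 against the 15 to 18 g/day of the Introduction and conclude that the diary misses 30/48 = 63% to 30/45 = 67% of fibre at Visits 2 and 4. The documents do not support that figure. They do not say that sachets are left out of the diary. The 15 to 18 g is a general average, not these women's intake. The sum also counts every gram of product as fibre and does not separate the fibre blend from the cellulose placebo. Moreover, if sachets are uncoded and diet is stable, an unmodelled product effect adds noise to the outcome and can lower the rejection rate (in simulation from about 8% to 5 to 7%). The mixing is a possibility to be closed off, not a bias of known size or direction.

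Finally, these are secondary associations in an exploratory pilot. That limits the consequences, but the plan still attaches p<0.05 to them.

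**Conclusion.** The point holds in conditional form. The defect is an undefined unit of analysis with no provision for repeated visits, relatives or product.

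- **Visits pooled, both variables correlated within woman:** p-values are too small. True error is about 8% to 22% over woman ICCs of 0.3 to 0.7, and up to about 28% with substantial family variance as well.
- **One row per woman across generations:** the excess is negligible at family ICC 0.1, and the error reaches 8 to 11% only at 0.5.
- **One visit within a generation:** no inflation.

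All sizes rest on assumed ICCs. The plan should be changed before analysis, because the remedy is cheap and the present wording leaves the choice open.

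**What to change.** Replace the plain correlations in Section 11 with a linear mixed model, on ranks or transformed values where data are skewed, with:

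- random intercepts for family and for woman within family;
- fixed terms for generation, product (none at Visits 1 and 3, fibre, cellulose) and period;
- diet split into the woman's own mean and her visit-specific deviation, so that between-woman and within-woman associations are reported separately;
- Kenward-Roger or Satterthwaite degrees of freedom, because there are only 10 families.

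Generation is needed because the Introduction states that younger people eat less fibre and hypothesises that they produce less SCFA. Without the term, a diet-SCFA association could simply reflect generation.

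State whether sachet fibre is counted in the diary variable.

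If a simple correlation is preferred, use Visit 1 only. Either report it within each generation, or take p-values from permuting whole families among families of the same composition, since trios, mother-daughter duos and grandmother-granddaughter duos are not interchangeable. Within a generation there are at most 10 women, so |r| must reach 0.632.

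The cost is a few sentences in the plan and a little more code in R, which is already planned. No extra participants, visits or samples are needed. The drawback is wider intervals.

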NMR analysis will be done on urine and stool samples to examine and compare metabolic profiles between grandmothers, mothers and offspring and their changes from baseline to end of intervention. Multivariate data analysis, such as Principal Component Analysis will be used to examine and compare if there are chemicals that differentiate the profiles of grandmothers, mothers and offspring at baseline and at the end of intervention. Analyses will be done using the following software R, Matlab, Simca and Prism GraphPad.

Food diaries will be coded using the Dietplan software which will offer insight into participants dietary habits such as their macronutrient intake. The data will be analysed using ANOVA, t-tests in R and Prism GraphPad to examine potential differences and similarities between participants.

The PhD student will be assisted by [name] in analysing the data. She will only have access to anonymised data.

12. Withdrawal Criteria and Adverse Events

Withdrawal Criteria

The safety of the study participants takes priority. Any significant adverse event (as assessed by the researchers) will halt the study and the ethics committee and sponsor will be informed as per standard protocol. All adverse events will be recorded and investigators will review each adverse event as it arises. In addition, participants will be free to withdraw at any time and are not required to give a reason.

If one or two participant(s) of the study group decide(s) to withdraw or need(s) to be withdrawn from the study, the other participant(s) from the group can still continue to participate.

The researcher can withdraw the participant on any of the following grounds:

• Participant's request

- Participant is lost to follow-up
- Participant no longer fulfils the eligibility criteria during the study duration (e.g. participant becomes pregnant etc.)
- Participant develops a condition or illness that interferes with participant's ability to take part in the study
- The investigator reserves the right to withdraw participants in the interest of participant's safety and welfare
- The participant loses capacity to consent.

All data and samples that have been collected up to the withdrawal point will be analysed and used in the study. After withdrawal from the study, no more samples and data will be collected from the participant.

Adverse Event (AE): Any untoward medical occurrence in a patient or clinical study subject.

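### No whole-community fibre-versus-placebo test is named for gut microbiota composition, and none for the NMR profiles

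*Combined protocol and SAP*

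**What the plan says.** Section 5 (Secondary Outcomes) lists first: "Comparison of gut microbiota composition from baseline to the end of the intervention between grandmothers, mothers and daughters between dietary fibre intervention and placebo". It lists next: "Comparison of metabolic profiles of urine and stool samples from baseline to the end of intervention between grandmothers, mothers and daughters", again between fibre and placebo.

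Section 11 (Statistical Analysis) treats composition in one paragraph: "Species diversity and richness will be calculated and statistical tests include t-tests and Mann-Whitney U tests", with significance at p<0.05. The generation comparison follows: "Species diversity and richness and their changes from baseline between grandmother, mother and offspring will be compared". The paragraph ends by saying that placebo and fibre data will be compared, without naming a measure or a test.

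Two other statements in Section 11 bear on this. Its opening sentence gives ANOVA and t-tests, paired and unpaired, for comparing participant groups, fibre and placebo, and names no outcome. It then adds correlations, and "linear models will be used to analyse the relationship between gut bacteria taxa, short-chain fatty acids levels, metabolites levels, food diary information and demographics".

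For the NMR profiles of urine and stool: "Multivariate data analysis, such as Principal Component Analysis will be used to examine and compare". That sentence goes on to name the generations and the two time points (baseline and end of intervention), but not the product.

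**The concern.** The outcome is which organisms are present and in what proportions. The measures named for it summarise how many taxa there are and how evenly they are spread. Richness, Shannon and Simpson do not use the identity of the taxa, so they can miss a shift from one set of dominant taxa to another. If fibre produced such a shift, the analyses written for this outcome could report no change. Any test that did show it would have to be chosen later, possibly after the data had been seen.

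The design adds a second issue. Every woman takes both products, so fibre against placebo is a within-woman comparison. The composition paragraph does not say whether its t-tests are paired, and Mann-Whitney U is an unpaired test.

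**Working it through.** The documents give no power or sample-size calculation (Section 8 says none is possible), so there is no planned figure to reproduce. The check is a reading of the plan, followed by illustrations on stated assumptions.

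**1. Outcome against named analysis**

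| Question in Section 5 | What Section 11 names |
|---|---|
| Composition, by generation | Diversity and richness and their changes; t-tests, Mann-Whitney U |
| Composition, fibre versus placebo | To be compared; no measure or test given |
| Individual taxa | Correlations and linear models with SCFA, metabolites, diet and demographics; product not listed |
| NMR profiles, by generation | Multivariate analysis, PCA as the example |
| NMR profiles, fibre versus placebo | Not mentioned in the NMR paragraph |

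No between-sample distance test, differential-abundance test or false-discovery control appears in the document.

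**2. Can diversity stay fixed while composition moves?** Assume four taxa at p = (0.4, 0.3, 0.2, 0.1) before and q = (0.1, 0.2, 0.3, 0.4) after.
- Richness is 4 both times.
- Shannon H = −Σ p ln p = 0.367 + 0.361 + 0.322 + 0.230 = 1.28. The same four terms arise for q, so H is again 1.28.
- Bray-Curtis = ½ Σ|p − q| = ½ (0.3 + 0.1 + 0.1 + 0.3) = 0.40.

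**3. The same mechanism with sampling noise.** Assume five taxa at 0.40, 0.30, 0.15, 0.10 and 0.05, reversed under the other product, with Dirichlet noise (concentration 20) and 400 simulations. Shannon is 1.392 for both and Bray-Curtis is 0.55. A paired t-test on Shannon rejected in 4.5% of simulations with 20 pairs and 5.5% with 30, which is the nominal error rate. A paired permutation test on the whole composition rejected in 100% at both sizes. The shift was built to be large and neutral for diversity, so these are not power estimates for this trial.

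**4. Does the general ANOVA/t-test sentence fill the gap?** It could be applied to each taxon at p<0.05. With k independent taxa, none of which differs, the chance of at least one false positive is 1 − 0.95^k. That is 0.64 for k = 20, 0.92 for k = 50 and 0.99 for k = 100. The values of k are assumptions, because the document gives no number of taxa. Read this way, the plan has a taxon-level comparison but no error control.

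**5. Cost of an unpaired rank test on paired data.** Assume normal data, a shift of 0.5 SD and a two-sided 5% level.

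| Women | Within-woman correlation | Power, Mann-Whitney | Power, signed-rank |
|---|---|---|---|
| 20 | 0.5 | 26% | 53% |
| 20 | 0.3 to 0.7 | 24–29% | 42–76% |
| 30 | 0.5 | 43% | 73% |
| 30 | 0.3 to 0.7 | 43–45% | 59–92% |

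A repeat of the simulation agreed within about two percentage points. The document gives neither the shift nor the correlation.

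**The case against.** The strongest reply is that Section 11 is an open list. The tests are said to include those named, PCA is given as an example, and the opening sentence allows paired or unpaired t-tests for any outcome. Taxa and metabolite levels do enter models, and qPCR is planned alongside sequencing. All of this stands, and it rules out several stronger readings that a reader might infer:

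- *Composition is analysed only through diversity, and profiles only through PCA.* Taxa and metabolites also enter correlations and linear models. Generation might reasonably count among the demographics there.
- *A shift in composition cannot be detected.* The sequencing data would show it, and the general sentence permits taxon-level tests. What is missing is a named test.
- *The hypothesis predicts replacement of taxa at constant diversity.* Section 2 speaks only of differential responses in composition. The rationale in Section 1 centres on diversity and loss of taxa, so diversity and richness are relevant measures, though not sufficient ones.
- *Mann-Whitney is assigned to the within-woman comparison.* The plan does not say this. It names no paired rank test and leaves the choice open.
- *PCA will be dominated by stable differences between women.* The plan does not say whether PCA uses raw values or changes, so this cannot be judged.

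The exact reversal of abundances is also a special case, and the plan names no diversity index. The example assumes the usual indices that ignore relatedness between taxa. It shows what can happen, not how likely it is here.

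**Conclusion.** The point holds as under-specification. For composition, the plan names no whole-community comparison of fibre with placebo and no generation-by-product test. For NMR profiles, it names a descriptive method in a sentence that omits product. Where taxa or metabolites might be tested one by one, no multiplicity control is described.

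The size cannot be given for this trial, because the document has no effect sizes, variances or taxon counts. Under the assumptions shown, a diversity-neutral shift with Bray-Curtis 0.40 leaves Shannon and richness unchanged. An unpaired rank test used within women would give up roughly 13 to 49 percentage points of power: 42 − 29 = 13 at the lowest correlation with 20 women, and 92 − 43 = 49 at the highest with 30. Importance is moderate, since these are secondary outcomes of an exploratory pilot with 20 to 30 women. The primary SCFA comparison is not affected.

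**What to change.** In Section 11, keep diversity and richness, and add the following:

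1. **Fibre versus placebo, composition.** PERMANOVA on Bray-Curtis or Aitchison distance, permuting product labels within woman. This matches Section 7, which randomises participants to an order. State how the baselines at Visits 1 and 3 enter. With Aitchison distance, changes from baseline can be taken on log-ratios, given a stated rule for zero counts. A Bray-Curtis comparison of end-of-intervention samples alone would not adjust for baseline.
2. **Generation by product.** For each woman, take the fibre-minus-placebo difference in change from baseline, for example on log-ratio-transformed abundances. Test it by permuting generation labels within family. Ten families, even if all are duos, give 2^10 = 1,024 label arrangements, enough for a test at 0.05. A family reduced to one woman by withdrawal contributes nothing to this test.
3. **NMR profiles.** Apply the same two restricted permutation tests, with PCA as the plot.
4. **Within-woman comparisons.** Specify paired t-tests or the Wilcoxon signed-rank test in place of Mann-Whitney U.
5. **Taxon-by-taxon tests.** Control the false-discovery rate and report the number of taxa tested.

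The text should be fixed before unblinding. It needs no new samples, visits or assays, and R is already planned. The cost is a little more analysis work.
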